 - ii) The wearable group will exhibit greater desired body composition changes more rapidly than the control group
 - iii) The wearable group will less post-operative complications than the control group

4) Administrative Organization

- a) This study will solely be completed at the University of Iowa Healthcare and Clinics Department of Orthopaedics and Rehabilitation.

5) Study Design

- a) Experimental design of the study: randomized controlled trial with single blinding
- b) Study population general description
 - i) Specify total number of adult subjects, age range and percent by gender
 - (1) 90 subjects (>18 years old)
 - (2) 50% male, 50% female
 - ii) Specify total number of minor subjects (less than 18 years of age), age range and percent by gender.
 - (1) none
- c) Sample size determination and power analyses
 - i) A power analysis was performed by the orthopedic department statistician [name].
- d) Study outcomes/endpoints
 - i) Primary outcomes
 - (1) Muscle mass, body mass, and fat mass changes from baseline at 3-, 6-, 9-, and 12-months
 - ii) Secondary outcomes
 - (1) Time to achieve desired body composition changes
 - (2) Time to TJA indication
 - (3) Surgical outcomes for those that undergo TJA

6) Study Procedures

- a) Describe Subject selection procedures
 - i) Describe the sampling plan including Inclusion/Exclusion criteria (subject and disease characteristics)
 - (1) Inclusion Criteria
 - (a) Adults > 18 years
 - (b) BMI > 40kg/m2
 - (c) Presenting to arthroplasty-obesity clinic with desire for total joint arthroplasty procedure
 - (d) Owns a smartphone capable of handling iOS or Google Play apps
 - (2) Exclusion Criteria
 - (a) Has a pacemaker or other electronic pacemaker placement
 - (b) Inability to complete study protocols
 - (c) Inability to stand unsupported for 60-90 seconds
 - ii) Indicate if the study plans to enroll non-English speaking subjects. If so, specify language(s), who will translate documents, who will serve as a translator. The IRB must review and approve all translated documents.
 - (1) This group will not be enrolled
 - iii) Indicate if the study will enroll subordinates of the PI or a member of the research team.
 - (1) This group will not be enrolled
 - iv) Indicate if the study will enroll pregnant women for research on fetuses and neonates
 - (1) This group will not be enrolled

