 - (a) Patients will be provided a BIA wearable (InBody BAND 2) and instructions regarding downloading smartphone app. Education regarding the device and app will be provided. In addition, they will receive the standard procedures/education provided in arthroplasty-obesity clinic
 - (2) Control group
 - (a) They will receive the standard procedures /education provided in arthroplasty-obesity clinic
- g) Describe all study assessments and activities
 - i) Provide a thorough, detailed description
 - (1) Randomization
 - (a) Once enrolled, patients will be randomized by a non-PI study member. Randomization will occur after the clinic standard education as to not be influenced based on randomization group.
 - (2) All patients
 - (a) All patients will experience a “coaching” period and be eligible for a “surgical period”. All patients (study and control) will undergo the clinic standard operating procedures of stationary BIA, hand-grip strength, and exercise and nutritional education (weight/resistance training, low carbohydrate/high protein diet) in the “coaching” period. All patients will also be advised of the goal to maintain or lose body mass, lose body fat, and gain muscle mass, which is also clinic standard operating procedure. Patients will follow-up in the clinic per standard protocol at approximately every 3 months (± 1 month). At each visit, stationary BIA, hand-grip strength, and exercise and nutritional coaching will be repeated, as is standard in clinic. All patients will be eligible to be indicated for TJA at the PI’s discretion. Per clinic procedures, patients are indicated for TJA as they achieve their body composition goals (maintain or lose body mass, lose body fat, and gain muscle mass). All patients will be instructed to not discuss their study arm (wearable or control) with the PI. Patients are eligible to enter the surgical period at any point during the coaching period. If patients feel that they meet their goals prior to they are eligible to reschedule their appointment sooner than the next visit. All patients will receive a phone call from a study team member every 1 month to assess compliance with study arm and check in on perceived progress.
 - (3) Wearable group

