 - (a) If patients are randomized the wearable group, they will be provided a wearable and instructions on installing the app and its features. They will be instructed to take BIA measurements at least weekly via the wearable. The wearable group will be instructed at the beginning of each visit to remove and keep their wearable out of sight of the PI during their visit.
 - (4) Patients who enter “Surgical” period

- (a) Patients who are indicated for TJA (at the PI's discretion) will leave the coaching period and enter the surgical period. Patients' medical record will be followed if they are indicated for TJA for post-operative outcomes such as infection, reoperation, implant failure. Surgical follow-up will occur for up to 24 months following study enrollment.
- ii) Provide a schedule of all study assessments and subject activities, including a tabular representation or timeline as applicable
 - (1) See **Table I** below
- h) Recontacting Subjects Lost to Follow Up – Indicate if the researcher will attempt to locate subjects if the research team is unable to reach them through the contact information they provided. Describe the procedures and justification for these efforts to locate subjects.
 - i) Research members will not contact the patients lost to follow, as standard clinic procedures have nursing staff contact the patients.
- i) Subject Compensation
 - i) Specify compensation method(s)
 - (1) Patients will not be compensated monetarily. Those randomized to the study cohort will be able to keep their wearable device, if desired.
 - ii) Describe the compensation plan, including amount per visit, total compensation amount, pro-rating for early withdrawal
 - (1) N/A
 - iii) Indicate whether the study will use the departmental cash handling plan or obtain approval from Accounting Services for a study-specific cash handling plan.
 - (1) N/A

7) Privacy and Confidentiality Protections

- a) Describe privacy protections – collecting data in a private space, collecting the amount and type of information you need to answer your research question(s)
 - i) Only the minimum necessary data will be collected. The data collected will be done in a private clinic room.
- b) Describe plans and justification for collecting social security number (SSN)
 - i) N/A

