Group sample sizes of 44 in the treatment and control arm achieve 80% power to detect a difference of 1.676 in a design with 5 repeated measurements having a compound symmetry covariance structure when the standard deviation is 3.610, the correlation between observations on the same subject is 0.500, and the alpha level is 0.050

11) Tables and Figures

Table I. Schedule of study procedures.

Study Period	Coaching ^a													Surgical ^a
	V1	V2	V3	V4	V5	V6	V7	V8	V9	V10	V11	V12	V13	
Visit Number	0	1	2	3	3	4	6	7	8	9	10	11	12	Until Month 24
All Patients														
Screening	X													
Consent	X													
Randomization	X													
Clinic Education ^b	X			X			X			X				X
Stationary BIA ^b	X			X			X			X				X
Handgrip Strength ^b	X			X			X			X				X
Phone Visit		X	X		X	X		X	X		X	X		
Wearable Group														
Wearable Distribution	X													
Wearable Compliance Check		X	X	X	X	X	X	X	X	X	X	X	X	
Surgical Outcomes Check^c														
^a Patients may exit the Coaching period and enter the Surgical period at any time point														
^b Standard protocol for all patients presenting to arthroplasty-obesity clinic														
^c Only for study group														
^d Only for subjects that undergo TJA. Will occur via EMR rather than direct patient contact.														

12) Literature Citations

1. Obesity: preventing and managing the global epidemic. Report of a WHO consultation. World Health Organ Tech Rep Ser 894: i, 2000
2. Obesity and total joint arthroplasty: a literature based review. In: J Arthroplasty. United States: 2013 Elsevier Inc. 714. 2013

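### Table I's footnote marker limits the Surgical Outcomes Check to the wearable arm, contradicting the text and hypothesis iii; probably a slipped marker, but it should be reconciled

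*Combined protocol and SAP*

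**What the plan says.** Table I lists the row as "Surgical Outcomes Check^c", and footnote c reads "Only for study group". Footnote d reads "Only for subjects that undergo TJA. Will occur via EMR rather than direct patient contact", but no row in the table carries a d.

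The text of section 6 sets no limit by arm. Section 6 g) i) (2) says "All patients will experience a “coaching” period and be eligible for a “surgical period", and then "All patients will be eligible to be indicated for TJA at the PI’s discretion". Section 6 g) i) (4) says "Patients' medical record will be followed if they are indicated for TJA for post-operative outcomes such as infection, reoperation, implant failure", with follow-up to 24 months after enrollment.

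Hypothesis iii in section 3 b) is "The wearable group will less post-operative complications than the control group". Section 5 d) ii) lists surgical outcomes among patients who have TJA as the third of three secondary outcomes, for the whole trial population. Section 10 a) i) plans to compare the secondary outcome between the treatment groups.

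**The concern.** Section 6 g) ii) names Table I as the schedule of all study assessments, so it is the page that staff are likely to work from. Read as printed, it tells them to check surgical outcomes in the wearable arm and is silent on controls. The text and the hypothesis need both arms.

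At stake is equal ascertainment of infection, reoperation and implant failure. If one arm is searched systematically and the other is not, more events will be found in the searched arm whatever the true rates are. Here that would count against the wearable arm, the opposite direction to hypothesis iii. Section 9 (safety monitoring) is marked as not applicable, so no separate safety process is described that would pick up complications in controls.

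**Working it through.** The plan gives no figure on this point. Its one power calculation, in section 10 b), does not concern surgical outcomes and is unaffected. The check is a comparison of passages.

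1. **What footnote c means.** The abstract calls the arm that receives the wristband the study group. Section 6 g) i) (2) contrasts study with control patients. Section 6 i) lets the study cohort keep the device. Footnote c therefore means the wearable arm.

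2. **What each footnote fits.** Footnote c restricts by arm. It fits the wearable distribution and wearable compliance rows, which carry no marker. Footnote d restricts by operation and names the medical record as the source. Of all the rows, it fits only the Surgical Outcomes Check. The table thus has one marker on a row that it does not suit and one footnote with no row. Putting d on this row and c on the wearable rows would make everything consistent.

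3. **Table against text.**
   - Table I as printed: check in the wearable arm only.
   - Section 6 g) i) (2): all patients can enter the surgical period.
   - Section 6 g) i) (4): record follow-up for anyone indicated for TJA, either arm.
   - Section 5 d) ii) (3): secondary outcome with no restriction by arm.
   - Section 3 b) iii): a comparison between arms.
   - Section 10 a) i): a comparison between arms.

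   All five places outside Table I point the same way, and Table I stands alone.

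4. **Direction of the bias if Table I were followed.** Let p be the true complication rate, taken as equal in both arms, and let s be the share of events found, with subscripts W (wearable) and C (control). The observed ratio is (p × s_W)/(p × s_C) = s_W/s_C. It equals 1 only when the search is the same in both arms, and it exceeds 1 whenever controls are searched less. The documents give no complication rate, no expected number of TJA patients and no detection rate, so the direction is known but the size is not.

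5. **What carries no weight.** In the text available the row shows no X in any column, which may be a loss in reading the table from PDF. Its place below the Wearable Group heading points the same way as marker c, but it too depends on a layout that may not have survived extraction.

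**The case against.** The strongest reply is that the protocol already handles this. Section 6 g) i) (4) sets out record follow-up independently of Table I and for either arm, so the schedule is not the only route to the outcome. The orphaned footnote d shows what the authors most likely meant. A misread of c for d in the PDF text cannot be excluded. The trial runs in one department (section 4) and the outcomes come from the medical record without patient contact, so control events missed at first could still be recovered. All of this stands, and it is why the point is minor.

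A reader might go further and infer that the trial would have no control data for hypothesis iii, or that the plan chose to follow one arm only. The documents support neither. The first holds only if Table I overrides section 6 and nobody goes back to the records. Nothing in the text suggests the second. Nor can the loss be expressed as a share of all control patients, since only those who have TJA can have surgical outcomes and the protocol does not project that number.

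What the reply does not remove is the contradiction. That records can be retrieved does not mean that they will be searched in the same way, and the schedule of assessments currently names one arm.

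**Conclusion.** The point holds as an internal inconsistency. The marker printed in Table I is wrong against section 6, the secondary outcome, hypothesis iii and the analysis plan. Severity is minor: one of three secondary outcomes is affected, the primary outcomes are not, and the error is recoverable. The bias, if Table I were followed, would run against the wearable arm, by an amount that the documents do not allow one to compute.

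This rests on two assumptions: that the marker in the sponsor's own file is c, as in the text available, and that staff might use Table I without section 6. If the source file shows d on this row, the contradiction over which arm is checked disappears.

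**What to change.** - Check Table I in the source file of the protocol.
- If it prints c, attach footnote d to the Surgical Outcomes Check instead, and confine footnote c to the two wearable rows or delete it.
- Take the row out from under the Wearable Group heading.
- Add one sentence, in section 6 g) i) (4) or under the table, that the same medical-record search to month 24 is run for TJA patients in both arms.
- If any search has already been done from Table I, repeat it for the control patients who had TJA.

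The cost is one table correction and one sentence in the next protocol version. Record review of control patients is already implied by section 6, so no new data collection is added.

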Protocol Title: Wearable Bioimpedance Analyzer for Tracking Body Composition Changes: A Randomized Controlled Trial

Protocol Version: 1.1

Protocol Date: 8/1/22

Principal Investigator: [name], PhD

Research Team: [name], [name], [name]

1) Abstract

- a) Obesity, namely at body mass index (BMI) levels exceeding $40\text{kg}/\text{m}^2$ (class III obesity), is a risk factor for many diseases including osteoarthritis (OA). In arthroplasty, patients in this population frequently present for and are turned away from surgical intervention. Subsequently, efforts are made to decrease BMI through simple weight loss, yet these have been suggested as ineffective and counterproductive. Furthermore, simple weight loss may include muscle mass loss, which is an additional risk factor for surgery. In our clinic, efforts have been made to encourage muscle mass gain and body fat loss over simple weight loss where progress has been tracked through stationary, multi-frequency bioimpedance analysis (BIA). BIA is a readily available technology offered to industry and consumers, and BIA has recently been incorporated into wearable devices. In our department, a novel clinic aimed at holistically serving the osteoarthritic-class III obese population for controlled and monitored weight loss through BIA.

This study, a randomized controlled trial, aims to recruit adult patients with class III obesity presenting to the arthroplasty-obesity clinic. While all patients will receive individual body composition coaching to increase muscle mass and decrease body fat mass, they will be randomized to one of two cohorts: the study group will receive a wearable BIA wristband (InBody BAND 2) and instruction on its use in addition to the standard coaching, and the control group will only receive the standard coaching.

This study aims to identify if the use of a wearable BIA wristband aids in the desired body composition changes. In addition, this study aims to quantify the body composition changes exhibited by each cohort. Finally, this study aims to track surgical outcomes for those patients that are indicated for total joint arthroplasty.

2) Background and Significance/Preliminary Studies

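### Surgical outcomes are taken only from the EMR, without patient contact, and the plan does not cover care received elsewhere, so events may be missed

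*Combined protocol and SAP*

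**What the plan says.** Section 4 places the whole trial at one institution: "This study will solely be completed at the University of Iowa Healthcare and Clinics Department of Orthopaedics and Rehabilitation".

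Section 6(g)(i)(4) gives the source of surgical outcomes: "Patients' medical record will be followed if they are indicated for TJA for post-operative outcomes such as infection, reoperation, implant failure". It also sets the window: "Surgical follow-up will occur for up to 24 months following study enrollment". Footnote d of Table I restricts the check to subjects who undergo TJA and adds that it "Will occur via EMR rather than direct patient contact".

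Section 6(g)(i)(2) provides for patient contact of another kind: "All patients will receive a phone call from a study team member every 1 month to assess compliance with study arm", and to ask about perceived progress. Table I shows phone visits in the coaching columns only. Under section 6(h) the research team does not contact patients lost to follow-up; clinic nursing staff do.

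Section 5(d) lists time to TJA indication and surgical outcomes among the secondary outcomes. Hypothesis iii expects fewer complications with the wearable. Section 10(a)(i) names a noninferiority comparison for primary and secondary outcomes and gives no margin.

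**The concern.** Reading outcomes from the record without asking the patient is a stated method, not just a missing detail. It finds only what reaches that record. The plan does not say whether the EMR shows encounters at other hospitals, how outside records would be obtained, or who would ask about outside care. An infection or reoperation handled elsewhere may then count as no event.

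The two descriptions of who is followed also differ. Section 6(g)(i)(4) follows patients indicated for TJA by the principal investigator, while footnote d covers those who undergo it. A patient operated on elsewhere without that indication belongs to the second set but not the first, and the plan has no rule for such a patient. For time to TJA indication, that surgery is a competing event: once it has happened, an indication for that joint may never follow, and the plan does not say how the patient's time is counted.

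At stake are the complication counts by arm and the handling of one time-to-event outcome.

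**Working it through.** **The plan's own figure.** Section 10(b) gives 44 per arm, 80% power, difference 1.676, SD 3.610, 5 measurements, correlation 0.500 and alpha 0.050. The SD of a subject's mean is 3.610 × √[(1 + 4 × 0.5)/5] = 2.796. Then n = 2 × (1.960 + 0.842)² × 2.796² / 1.676² = 43.7, rounded up to 44 (two-sided). Power at 44 per arm is 80.3%. The figure reproduces. It concerns body composition only, and this point does not touch it. The documents give no such calculation for surgical outcomes.

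**Assumptions.** The documents give no complication rate, number of TJAs or capture rate. I assume true risks of 20% (control) and 10% (wearable), no false positives, and 15, 30 or 45 operated patients per arm. The last is the ceiling: 90 / 2 = 45.

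**Equal capture s in both arms.** Recorded risk = true risk × s. The difference is s × 10 points. The ratio is 0.10s / 0.20s = 0.50 for any s.

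Power = Φ{[d − 1.96 × √(2p̄(1 − p̄)/n)] / √[(p₁(1 − p₁) + p₂(1 − p₂))/n]}, where d is the recorded difference and p̄ the mean of the two recorded risks. For s = 1 and n = 30: (0.10 − 1.96 × 0.0922) / 0.0913 = −0.884, and Φ(−0.884) = 18.8%.

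| Capture | Difference (points) | Risk ratio | Power, 15/arm | Power, 30/arm | Power, 45/arm | n/arm for 80% |
|---|---|---|---|---|---|---|
| 100% | 10 | 0.50 | 11.4% | 18.8% | 26.2% | 199 |
| 90% | 9 | 0.50 | 10.6% | 17.2% | 23.7% | 226 |
| 80% | 8 | 0.50 | 9.8% | 15.5% | 21.2% | 258 |
| 70% | 7 | 0.50 | 9.0% | 13.9% | 18.9% | 300 |
| 50% | 5 | 0.50 | 7.4% | 10.9% | 14.4% | 435 |

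**Unequal capture.**
- Control 90%, wearable 70%: 18% vs 7%, difference 11 points, ratio 0.39.
- Control 70%, wearable 90%: 14% vs 9%, difference 5 points, ratio 0.64.
- No true effect (15% in both arms), control 90%, wearable 70%: 13.5% vs 10.5%, a false ratio of 0.78. With the capture rates swapped, the false ratio is 1.29.

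**Noninferiority.** The upper 95% limit for wearable minus control is −d + 1.96 × √[(p₁(1 − p₁) + p₂(1 − p₂))/n].
- 44 per arm, full capture: −0.10 + 1.96 × √(0.25/44) = 4.8 points. At 60% capture (12% vs 6%): −0.06 + 1.96 × √(0.162/44) = 5.9 points.
- 30 per arm: 7.9 moves to 8.4 points.
- 15 per arm: 15.3 moves to 14.4 points.

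The limit rises in two cases and falls in the third, so the direction is not fixed.

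**The case against.** The strongest case against is that the documents say only medical record and EMR. They do not say that outside records are excluded, so a reader who infers that outside events are certainly missed goes beyond the text. That stands: the events may be missed, no more.

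Four other readings are tempting and are not supported.

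- **That under-capture makes the arms look alike.** Under equal capture this holds for the absolute difference, not for the risk ratio. Under unequal capture the difference can widen, narrow or appear from nothing.
- **That it pushes the comparison towards noninferiority.** If the wearable has fewer complications, as hypothesis iii expects, losing events shrinks its advantage, and the upper limit can move away from noninferiority, as shown above. A pull towards noninferiority is clear only if the wearable is truly worse. With no margin stated, no effect on the conclusion can be claimed.
- **That later BIA readings would be taken as non-surgical.** The patient would have to keep attending an arthroplasty clinic about every 3 months with a new joint that nobody noticed. The documents do not make that likely.
- **That the Abstract shows patients seeking surgery elsewhere.** Its remark that "patients in this population frequently present for and are turned away from surgical intervention" describes the wider population. It could equally mean that surgery elsewhere is hard to obtain.

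The consequence is also limited. Aim iii is only to track surgical outcomes, and no power is claimed for them. Even full capture would leave power at about 11% to 26% under the assumed rates. This keeps the point minor. It does not remove it, because the counts are still an outcome to be compared by arm.

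Finally, extra questions on the monthly calls alone would not reach operated patients, since Table I shows no phone visits in the surgical period. The callers check study-arm compliance and so probably know the allocation. Both facts shape the fix.

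**Conclusion.** The point holds as a cheap improvement. The plan sets EMR-only ascertainment without patient contact at one centre and is silent on care elsewhere, so complications and joint replacements elsewhere may be missed. Under the assumed 20% vs 10% and equal capture of 80%, the difference would be 8 rather than 10 points, and power at 30 per arm 15.5% rather than 18.8%, with the risk ratio unchanged. Unequal capture could bias the result in either direction. These sizes rest wholly on assumed rates. Better capture would not make the comparison conclusive: 199 operated patients per arm would be needed for 80% power. The primary outcome's sample size is unaffected. Surgery elsewhere remains an unhandled competing event for time to TJA indication, whatever its frequency.

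A separate reconciliation is needed in Table I. As extracted, the surgical outcomes check carries footnote c, which limits an item to the study group, and footnote d has no anchor. A reader might infer that only the wearable arm is checked. Section 6(g)(i)(4) does not support that, and the mismatch may be an extraction fault.

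**What to change.** 1. Amend footnote d so that the source is the EMR, including any outside records it can access, plus a scripted patient query. State what the EMR covers.
2. Add one identical question on joint replacement elsewhere to the existing monthly coaching calls in both arms. Record the date and treat it as a competing event for time to TJA indication.
3. Add one scripted closing call at month 24 to each patient who had TJA, in both arms, asking about treatment of the replaced joint elsewhere. Existing staff who do not know the allocation should make it where possible, so that prompting does not differ by arm.
4. Confirm reported events from records, and report events by source (EMR or patient report) and by arm.
5. Check the footnote letters in Table I against section 6(g)(i)(4), and reconcile that section's followed group (indicated) with footnote d's (operated).

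The cost is script wording and one short extra call per patient who had TJA. The downsides are reliance on recall and some outside records that cannot be obtained.
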